**Table 4 Induction Treatment for the *Follicular Lymphoma* Expansion Phase**

Cycle	G+Pola+Len (28-Day Cycles)
Cycle 1	
 
• Lenalidomide at the RP2D (mg) PO once daily on Days 1–21
 
• Obinutuzumab 1000 mg IV on Days 1, 8, and 15
 
• Polatuzumab vedotin at the RP2D (mg/kg) IV on Day 1
 

Cycles 2–6	
 
• Lenalidomide at the RP2D (mg) PO once daily on Days 1–21
 
• Obinutuzumab 1000 mg IV on Day 1
 
• Polatuzumab vedotin at the RP2D (mg/kg) IV on Day 1
 

*G + Pola + Len* = obinutuzumab in combination with polatuzumab vedotin and lenalidomide; IV=intravenous; PO=by mouth; RP2D=recommended Phase II dose.

Note: Treatments will be administered sequentially in the following order: lenalidomide, obinutuzumab, and polatuzumab vedotin.

Patients with FL who achieve a CR, PR, or stable disease at EOI will receive post-induction treatment (referred to as maintenance) with obinutuzumab and lenalidomide, as outlined in Table 5. Polatuzumab vedotin will not be given during the post-induction phase. Post-induction treatment should start 8 weeks ( $\pm 1$  week) after Day 1 of the final cycle of induction and will continue until disease progression or unacceptable toxicity, for up to 24 months for maintenance treatment.

**Table 5 Post-Induction Treatment for the *Follicular Lymphoma* Expansion Phase**

Patient Population	Regimen
Patients with FL	
Maintenance treatment consisting of the following, administered for approximately 24 months (from Months 1–24):
 
 
• Lenalidomide 10 mg PO once daily on Days 1–21 of each month for a maximum of 12 months
 
• Obinutuzumab 1000 mg IV on Day 1 of every other month (i.e., every 2 months), starting with Month 1 (i.e., Months 1, 3, 5, 7, 9, 11, 13, 15, 17, 19, 21, and 23) for a maximum of 24 months
 

FL = follicular lymphoma; IV = intravenous; PO = by mouth.

Notes: A month is defined as 28 days. Treatments will be administered sequentially in the following order: lenalidomide followed by obinutuzumab.

### 3.1.3 *Rituximab plus Polatuzumab Vedotin plus Lenalidomide Treatment Group (Patients with Relapsed or Refractory Diffuse Large B-Cell Lymphoma)*

*Based on the safety and efficacy results from the Phase III BO21005 study in patients with DLBCL, the protocol has been amended to explore dose-finding of lenalidomide in*

combination with fixed doses of polatuzumab vedotin and rituximab instead of obinutuzumab for patients with R/R DLBCL.

### **3.1.3.1 Dose-Escalation Phase**

The DLBCL dose-escalation phase will open with the purpose of identifying the RP2D for lenalidomide when combined with polatuzumab vedotin at 1.8 mg/kg and rituximab at 375 mg/m^2 as induction treatment in patients with R/R DLBCL. The dose escalation will initiate at the lenalidomide 10-mg dose level and increase through Cohorts A, B, and C (see [Figure 3](#)).

Approximately 12–18 patients will be enrolled in the R/R DLBCL dose-escalation phase. Cohorts of 3–6 patients each will be treated in accordance with the treatment regimens and dose-escalation rules described below.

Patients will be closely monitored for adverse events during the DLT assessment window, defined as the first treatment cycle (from Day 1 of Cycle 1 to Day 1 of Cycle 2). Adverse events meeting the criteria for DLT, as defined below (see [Section 3.1.2.1.1](#)), will be reported to the Sponsor within 24 hours (see [Section 5.4.2](#)).

Patients who discontinue from the study prior to completing the DLT assessment window for reasons other than a DLT will be considered non-evaluable for dose-escalation decisions and RP2D assessments and will be replaced by an additional patient at that same dose level. Patients who miss one or more doses of polatuzumab vedotin or rituximab or five consecutive daily doses of lenalidomide during the DLT assessment window for reasons other than a DLT will also be replaced and considered non-evaluable for dose-escalation decisions. Patients who receive supportive care during the DLT assessment window that may confound the evaluation of DLTs may be replaced at the discretion of the Medical Monitor.

Patients will receive induction treatment with R + Pola + Len for a total of six cycles. Patients achieving a CR or PR at EOI will be eligible to receive consolidation treatment with R + Len. A study schema is provided in [Figure 1](#).

### **Treatment Regimens for DLBCL Dose-Escalation Phase**

Patients enrolled in the DLBCL-dose-escalation phase will receive induction treatment, administered in 28-day cycles as shown in [Table 6](#). When study treatments are given on the same day, they will be administered sequentially in the following order: lenalidomide, rituximab, and polatuzumab vedotin.

**Table 6 Induction Treatment for the DLBCL Dose-Escalation Phase**

Cycle	R + Pola + Len (28-Day Cycles)
Cycles 1–6	
 
• Lenalidomide 10 mg, 15 mg, or 20 mg PO once daily on Days 1–21
 
• Rituximab 375 mg/m^2 IV on Day 1
 
• Polatuzumab vedotin 1.8 mg/kg IV on Day 1
 

IV = intravenous; PO = by mouth; R + Pola + Len = rituximab in combination with polatuzumab vedotin and lenalidomide.

Note: Treatments will be administered sequentially in the following order: lenalidomide, rituximab, and polatuzumab vedotin.

Patients who achieve a CR or PR at EOI will receive consolidation treatment with R + Len, as outlined in [Table 7](#). Polatuzumab vedotin will not be given as maintenance treatment. Consolidation treatment should start 8 weeks ( $\pm 1$  week) after Day 1 of Cycle 6 and will continue for 6 months until disease progression or unacceptable toxicity.

**Table 7 Consolidation Treatment for the Dose-Escalation Phase**

Patient Population	Regimen
Patients with DLBCL	
Consolidation treatment consisting of the following, administered for approximately 6 months (from Months 1–6):
 
 
• Lenalidomide 10 mg PO once daily on Days 1–21 of each month for a maximum of 6 months
 
• Rituximab 375 mg/m^2 IV on Day 1 of every other month (i.e., every 2 months starting with Month 1 (i.e., Months 1, 3, 5))
 

[figure not shown]
DLBCL = diffuse large B-cell lymphoma; IV = intravenous; PO = by mouth.

Notes: A month is defined as 28 days. Treatments will be administered sequentially in the following order: lenalidomide followed by rituximab.

### Dose-Escalation Rules

A standard 3 +3 dose-escalation schema will be used. The rituximab and polatuzumab dose levels will remain fixed during the dose-escalation phase, and only the lenalidomide will be dose escalated. The polatuzumab dose of 1.8 mg/kg is based on ongoing Phase II trials (see Sections 1.3.2 and 3.3.3.3). Inpatient dose escalation is not allowed. The overall DLBCL dose-escalation plan is depicted in [Figure 3](#).

**Figure 3 DLBCL Dose-Escalation Plan**

If Cohort A doses are deemed safe and tolerable, escalation will continue with enrollment of Cohort B.

If Cohort B doses are deemed safe and tolerable, escalation will continue with enrollment of Cohort C.

**Table 8 DLBCL Dose-Escalation Cohorts**

Cohort	Rituximab a	Polatuzumab Vedotin b	Lenalidomide c
A	375 mg/m 	1.8 mg/kg	10 mg
B	375 mg/m 	1.8 mg/kg	15 mg
C	375 mg/m 	1.8 mg/kg	20 mg

DLBCL = diffuse large B-cell lymphoma; IV = intravenous; PO = by mouth.

a Rituximab will be administered at a dose of 375 mg/m^2 IV on Day 1 of each 28-day cycle of induction.

b Polatuzumab vedotin will be administered at a dose of 1.8 mg/kg IV on Day 1 of each 28-day cycle of induction.

c Lenalidomide will be administered at doses of 10 mg, 15 mg, or 20 mg PO once daily on Days 1–21 of each 28-day cycle.

Dose escalation will occur in accordance with the rules listed below.

- A minimum of 3 patients will initially be enrolled in each cohort. The first 3 patients in each cohort will be sequentially enrolled and dosed at least 48 hours apart.
- If none of the first 3 DLT-evaluable patients experiences a DLT, the doses in that cohort will be deemed safe and tolerable, and escalation may continue per the dose-escalation plan described above.

- *If 1 of the first 3 DLT-evaluable patients experiences a DLT, the cohort will be expanded to 6 patients. If there are no further DLTs in the first 6 DLT-evaluable patients, the doses in that cohort will be deemed safe and tolerable, and escalation may continue per the dose-escalation plan described above.*
- *If a DLT is observed in  $\geq 33\%$  of patients (e.g., 2 or more of up to 6 DLT-evaluable patients), the dose combination at which this occurs will be considered intolerable and the MTD will have been exceeded for lenalidomide in the R + Pola + Len treatment combination.*
- *If the MTD is exceeded in any cohort, the highest dose combination at which  $< 33\%$  of patients (e.g., 2 of 6 DLT-evaluable patients) experience a DLT will be declared the combination MTD (i.e., the MTDs lenalidomide in the R + Pola + Len treatment combination).*
- *If the MTD is not exceeded at any dose level, the highest dose combination administered in this study will be declared the maximum administered dose for polatuzumab vedotin and lenalidomide in the R + Pola + Len treatment combination.*

*If the MTD is exceeded in any cohort, de-escalation of the lenalidomide dose and/or polatuzumab vedotin dose, and/or adjustment of treatment schedules (e.g., lenalidomide treatment on Days 1–10) may occur. Additional patients may be enrolled in a given cohort in the absence of DLTs to acquire additional safety data for the appropriate dose levels in the expansion phase of the study.*

*On the basis of a review of real-time safety data and available preliminary PK data, dose escalation may be halted or modified by the Sponsor as deemed appropriate.*

*Relevant demographic, adverse event, laboratory, dose administration/intensity, and PK (if available) data will be reviewed prior to dose-escalation decisions, which will be objectively reviewed throughout the study by the Clinical Study Team and prior to dose-escalation decisions, which will be made by the Medical Monitor in consultation with the Principal Investigator and participating investigators.*

*Although the DLT assessment window is defined as the first treatment cycle, cumulative or late toxicities occurring beyond the first cycle may be considered when determining the RP2Ds. Prior to opening the R/R DLBCL expansion phase, the Clinical Study Team and the Medical Monitor will review the cumulative data, determine the RP2D, and review this with the IMC for approval.*

### **3.1.3.2 DLBCL Expansion Phase**

*The expansion phase is designed to further assess the safety and efficacy of lenalidomide when combined with a fixed dose of rituximab and polatuzumab vedotin in DLBCL patients.*

*Approximately 40 patients with DLBCL will be enrolled during the expansion phase and treated as described below.*

All patients enrolled in the expansion phase will receive induction treatment as outlined in [Table 9](#). When study treatments are given on the same day, they will be administered sequentially in the following order: lenalidomide, rituximab, and polatuzumab vedotin.

**Table 9 Induction Treatment for the DLBCL Expansion Phase**

Cycle	R + Pola + Len (28-Day Cycles)
Cycles 1–6	
Lenalidomide 10 mg, 15 mg, or 20 mg PO once daily on Days 1–21
 
Rituximab 375 mg/m^2 IV on Day 1
 
Polatuzumab vedotin 1.8 mg/kg IV on Day 1

DLBCL = diffuse large B-cell lymphoma; IV = intravenous; PO = by mouth; R + Pola + Len = rituximab in combination with polatuzumab vedotin and lenalidomide.

Note: Treatments will be administered sequentially in the following order: lenalidomide, rituximab, and polatuzumab vedotin.

Patients with DLBCL who achieve a CR or PR at EOI will receive post-induction treatment (referred to as consolidation) with rituximab and lenalidomide as outlined in [Table 10](#). Polatuzumab vedotin will not be given during the post-induction phase. Post-induction treatment should start 8 weeks ( $\pm 1$  week) after Day 1 of the final cycle of induction and will continue until disease progression or unacceptable toxicity, for up to 6 months for consolidation treatment.

**Table 10 Post-Induction Treatment for the DLBCL Expansion Phase**

Patient Population	Regimen
Patients with DLBCL	
Consolidation treatment consisting of the following, administered for approximately 6 months (Months 1–6):
 
 
• Lenalidomide 10 mg PO once daily on Days 1–21 of each month, for a maximum of 6 months
 
• Rituximab 375mg/m^2 IV on Day 1 of every other month (i.e., every 2 months) starting with Month 1 (i.e., Months 1, 3, 5)
 

DLBCL = diffuse large B-cell lymphoma; IV = intravenous; PO = by mouth.

Notes: A month is defined as 28 days. Treatments will be administered sequentially in the following order: lenalidomide followed by rituximab.

### 3.1.4 Internal Monitoring Committee

An IMC will monitor patient safety throughout the study. The IMC will include, but will not be limited to, Roche representatives from Clinical Science, Drug Safety, Biostatistics, and Statistical Programming and Analysis. In addition to the ongoing assessment of the incidence and nature of adverse events (particularly Grade  $\geq 3$  events), serious adverse

events, deaths, and laboratory abnormalities performed by the investigator and the Medical Monitor, the IMC will review all necessary cumulative data at regular intervals during the study. At the time of each review, the IMC will make appropriate recommendations (e.g., the study should continue as planned, additional analyses should be performed, or enrollment should be held pending further safety evaluations). Decisions will be made in consideration of the totality of the available data. Ad hoc meetings may be called in addition to scheduled meetings, as necessary, to provide recommendations on management of any potential new safety signals. Specific operational details such as the committee's composition, frequency and timing of meetings, members' roles and responsibilities, and data to be reviewed will be detailed in an IMC charter.

### **3.1.5 Independent Review Committee**

An IRC will assess all patients for response on the basis of imaging results and bone marrow biopsy results. The IRC will consist of radiologists, nuclear medicine experts, and a board-certified oncologist with experience in malignant lymphoma. Specific methodological and operational details will be specified in an IRC charter.

### **3.1.6 Post-Treatment and Survival Follow-Up**

Patients who complete treatment or discontinue treatment for reasons other than disease progression will undergo assessments every 3 months during the post-treatment follow-up period, which will continue until disease progression, the start of new anti-lymphoma treatment, or the end of the study (as defined below), whichever occurs first. Patients who experience disease progression will be evaluated for survival status and initiation of new anti-lymphoma treatment every 3 months until the end of the study. Details are provided in the schedules of assessments (see [Appendix 1](#) and [Appendix 2](#)).

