## **3.2 END OF STUDY AND LENGTH OF STUDY**

The end of this study is defined as the time when both of the following criteria are met:

- All enrolled patients with FL have *been followed for at least 90 days after they have completed or discontinued study treatment (including induction treatment and maintenance treatment as applicable)*.
- All enrolled patients with DLBCL have been followed for at least 1 year after they have completed or discontinued study treatment (including induction treatment and consolidation treatment as applicable).

The total length of the study, from screening of the first patient to the end of the study, is expected to be approximately 5 years.

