#### **5.3.1 Adverse Event Reporting Period**

Investigators will seek information on adverse events at each patient contact. All adverse events, whether reported by the patient or noted by study personnel, will be recorded in the patient’s medical record and on the Adverse Event eCRF.

**After informed consent has been obtained but prior to initiation of study treatment**, only serious adverse events caused by a protocol-mandated intervention (e.g., invasive procedures such as biopsies, discontinuation of medications) should be reported (see Section 5.4.2 for instructions for reporting serious adverse events).

**After initiation of study treatment**, all adverse events will be reported until 90 days after the last dose of study treatment. After this period, the investigator should report any serious adverse events that are believed to be related to prior study treatment *and events of second malignancies for patients who received obinutuzumab* (see Section 5.6).

An exception is *for the FL patients, where* Grade 3 and 4 infections (both related and unrelated) should be reported until up to 2 years after the last dose of *obinutuzumab*.

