### Schedule of Assessments for Patients with Follicular Lymphoma (cont.)

---

- informed consent and within the defined window may be used as screening and baseline assessments; such tests do not need to be repeated for screening purposes.
- b Patients who complete maintenance treatment or discontinue maintenance treatment prematurely will undergo assessments at EOM.
  - c EOI assessments should be performed 6–8 weeks after Day 1 of the last induction cycle. As an exception, patients who discontinue induction treatment prematurely because of an adverse event may undergo EOI assessments 4–8 weeks after their last dose of study treatment.
  - d Patients who complete treatment or discontinue treatment for reasons other than disease progression will undergo assessments every 3 months during the post-treatment FU period, which will continue until disease progression, the start of new anti-lymphoma treatment, or the end of the study, whichever occurs first. The first post-treatment FU visit is 3 months after the EOI visit for patients who do not receive maintenance treatment and 3 months after the last dose for patients who receive maintenance treatment. Patients who experience disease progression will undergo limited assessments every 3 months during the survival FU period, which will continue until the end of the study. The end of the study is defined as the time when all enrolled patients have completed or discontinued study treatment or when the Sponsor ends the study.
  - e Informed consent must be documented before any study-specific screening procedure is performed.

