### Schedule of Assessments for Patients with Diffuse Large B-Cell Lymphoma (cont.)

---

Notes: On treatment days, all assessments should be performed prior to dosing, unless otherwise specified. Assessments shaded in gray should be performed as scheduled, but the associated data do not need to be recorded on the eCRF (except in the case of an adverse event).

- a The screening period starts with the signing of the Informed Consent Form. Results of standard-of-care tests or examinations performed prior to obtaining informed consent and within the defined window may be used as screening and baseline assessments; such tests do not need to be repeated for screening purposes.
- b Patients who complete consolidation treatment or discontinue consolidation treatment prematurely will undergo assessments at EOC.
- c EOI assessments should be performed 6–8 weeks after Day 1 of the last induction cycle. As an exception, patients who discontinue induction treatment prematurely because of an adverse event may undergo EOI assessments 4–8 weeks after their last dose of study treatment.
- d Patients who complete treatment or discontinue treatment for reasons other than disease progression will undergo assessments every 3 months during the post-treatment FU period, which will continue until disease progression, the start of new anti-lymphoma treatment, or the end of the study, whichever occurs first. The first post-treatment FU visit is 3 months after the EOI visit for patients who do not receive consolidation treatment and 3 months after the last dose for patients who receive consolidation treatment. Patients who experience disease progression will undergo limited assessments every 3 months during the survival FU period, which will continue until the end of the study. The end of the study is defined as the time when all enrolled patients have completed or discontinued study treatment.
- e Informed consent must be documented before any study-specific screening procedure is performed.

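### Patients who start new therapy without documented progression have no scheduled survival follow-up, and footnote d of Appendices 1 and 2 contradicts Section 3.2 on the end of study (exploratory endpoints only)

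*Combined protocol and SAP*

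**What the plan says.** **Leaving post-treatment follow-up.** Under Section 3.1.6, patients who stop treatment without progression are seen every 3 months in a period "which will continue until disease progression, the start of new anti-lymphoma treatment, or the end of the study (as defined below"; the closing reference points forward to Section 3.2.

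**Entering survival follow-up.** The next sentence of Section 3.1.6 admits only patients with progression: "Patients who experience disease progression will be evaluated for survival status and initiation of new anti-lymphoma treatment every 3 months". Footnote d of the DLBCL schedule (Appendix 2) agrees: "Patients who experience disease progression will undergo limited assessments every 3 months during the survival FU period". Footnote d of Appendix 1 has the same rule for FL. Both grids place the survival row only in the survival column.

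**End of study.** For DLBCL, Section 3.2 and the synopsis require that "All enrolled patients with DLBCL have been followed for at least 1 year after they have completed or discontinued study treatment"; for FL they require at least 90 days. Footnote d of Appendix 2 says otherwise: "The end of the study is defined as the time when all enrolled patients have completed or discontinued study treatment". Footnote d of Appendix 1 sets the end at the time when "all enrolled patients have completed or discontinued study treatment or when the Sponsor ends the study".

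**Safety reporting.** Section 5.3.1 states that "all adverse events will be reported until 90 days after the last dose of study treatment". Section 5.3.5.8 covers deaths in that period and refers later deaths to Section 5.6.

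**Analysis.** Sections 2.2.3 and 6.6.3 list OS as exploratory. It counts death from any cause, is summarized by Kaplan-Meier, and censors survivors at the last date known alive.

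**The concern.** The exit rule has two clinical triggers, progression and new therapy. The entry rule for survival follow-up has only the first. The protocol expects patients in the gap: event-free survival (EFS) lists new therapy as a failure distinct from progression, DLBCL patients with stable disease at the end of induction (EOI) get no consolidation, and the toxicity rules end treatment without progression. If such a patient progresses later, the survival sentence would apply, but no scheduled tumor assessment remains to detect it.

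Deaths after a switch belong in OS. If they are not found, the patient is censored at the last contact. A switch may be linked to prognosis, so that censoring may be informative. Section 3.2 also promises a year of follow-up for every DLBCL patient, and the schedule gives this group no survival visit to deliver it.

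The end-of-study conflict is a separate matter. A site or data manager working from the appendices would read a shorter study than one working from Section 3.2. That would be administrative censoring, not informative censoring.

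**Working it through.** The plan states no figure on this point, so there is none to reproduce. The check compares the rules and then applies the calendar to one case.

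**Other routes by which a death might be captured after a switch**
- To 90 days after the last dose: all deaths (Sections 5.3.1 and 5.3.5.8).
- After that, Section 5.6: serious events the investigator learns of and believes related; second malignancies and Grade 3–4 infections in obinutuzumab patients; lymphoma deaths during survival follow-up, the period these patients do not enter.
- Section 4.6.1: public records on survival status, mentioned only in the consent-withdrawal text.
- Appendices 3 and 4: pharmacokinetic and immunogenicity samples after the last dose. Some FL entries at 1–2 years apply only if the patient is in clinic. The DLBCL rows sit under the consolidation heading.

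None of these is systematic survival follow-up.

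**Illustration: DLBCL, stable disease at EOI, switch at or soon after EOI.** Days are counted from the first dose, with 28-day cycles and no delays.
- Cycle 6 Day 1: 5 × 28 = Day 140.
- Last lenalidomide (Cycle 6 Day 21): 140 + 20 = Day 160.
- EOI visit, 6–8 weeks after Cycle 6 Day 1: 140 + 42 to 140 + 56 = Days 182–196.
- End of adverse event and death reporting: 160 + 90 = Day 250.
- First post-treatment visit. Footnote d says "The first post-treatment FU visit is 3 months after the EOI visit for patients who do not receive consolidation treatment". With 28-day months, 182 + 84 = Day 266; with calendar months, 196 + 91 = Day 287. The visit is not reached, because the switch has already ended the period.
- Section 3.2 minimum: 160 + 365 = Day 525.
- Covered: 90/365 = 25%. Not covered systematically: 525 − 250 = 275 days, and 275/365 = 75%.
- Appendix 4 samples, timed from the last antibody dose at Day 140: 140 + 120 = Day 260, then 140 + 365 to 140 + 730 = Days 505–870. Between the first two contacts: 505 − 260 = 245 days.

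**FL.** The reporting window and the Section 3.2 minimum are both 90 days, so the shortfall is 90 − 90 = 0. The gap is only relative to the 3-monthly checks given to patients with progression.

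**End of study.** Section 3.1.1 requires adverse event monitoring for at least 90 days after the last dose, whichever definition applies.
- Last DLBCL finisher: 365 days under Section 3.2, 90 under footnote d; loss 365 − 90 = 275 days.
- Last FL finisher: 90 against 90; loss 0.
- For a DLBCL patient completing consolidation, treatment starts at 140 + 56 = Day 196 and the last lenalidomide dose is at 196 + 5 × 28 + 20 = Day 356. Guaranteed follow-up runs to 356 + 365 = Day 721 under Section 3.2, close to the planned 2-year landmark, and to 356 + 90 = Day 446 under footnote d.

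**The case against.** The other side has several fair points.

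- **Section 3.2 already imposes the duty.** It requires a year for every DLBCL patient and makes no exception for switchers. That stands, but it sets an obligation without a visit or contact to meet it.
- **Reporting does not simply stop at 90 days.** Section 5.3.5.8 calls mortality an efficacy endpoint and sends later deaths to Section 5.6, and FL infections of Grade 3–4 are reportable for 2 years. A reader might infer that no later death could reach the database; the documents do not support that. What they show is a partial route that leaves out unrelated deaths and, for these patients, lymphoma deaths.
- **The switch is itself recorded.** The new-therapy row also appears in the post-treatment column, which supplies a last-known-alive date. That fixes the censoring date but does not find a later death.
- **Sampling visits are contacts.** The Appendix 4 rows carry no in-clinic limit, and the consolidation heading may be only a table divider. If they apply, they show survival at about Day 260 and again from Day 505, without a survival check in between.
- **The end-of-study conflict is editorial.** Section 3.1.6 points to Section 3.2, the synopsis agrees with it, and footnote d looks like text that was not updated. That limits the consequence; the contradiction remains in current text.
- **The worked case is chosen to show the gap.** That is so. The 25%/75% split describes that case only, not the cohort.

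**Conclusion.** Both parts hold, at minor severity. A patient who starts new therapy without documented progression has no scheduled survival follow-up, and footnote d contradicts Section 3.2 and the synopsis.

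Three stronger readings are tempting and should not be drawn:
- That footnote d leaves the last finisher with no follow-up at all. The 90-day safety period applies regardless, so the guaranteed loss is 275 days for DLBCL and essentially nothing for FL. Even that is a loss of the guarantee: if the definition spans both histologies, FL patients still on maintenance would keep the study open longer.
- That OS is biased by a known amount or in a known direction. The documents do not give the number of such patients or their prognosis; the censoring may be informative, and no more can be said.
- That the main result is at risk. The primary endpoint is complete response at EOI by independent review, and EFS already counts new therapy. The effect is confined to exploratory, descriptive endpoints, mainly OS.

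The day counts assume no treatment delays, take the end of treatment as the last lenalidomide dose, and place the switch at or soon after EOI.

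**What to change.** In Section 3.1.6 and in footnote d of both appendices, extend 3-monthly survival follow-up to any patient who either progresses or starts new anti-lymphoma therapy. Replace the end-of-study sentence in both footnotes with the Section 3.2 definition. The sponsor clause in Appendix 1 can go, since Section 4.6.3 already lets the sponsor terminate the study.

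The cost is a wording change in three places and a 3-monthly survival-status check for a minority of patients. No treatment rule, sample size or primary analysis changes. The fix captures deaths only: tumor assessments would still end at new therapy, so progression after a switch would remain unobserved.
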